9.3 Study procedures

[figure not shown]
After informed consent is obtained, assessment will be planned at the outpatient clinic of the LUMC. Questionnaires considering HRQoL, behaviour, allergies or infections will be sent home with the request to fill in the forms and bring them at the planned visit. We will

provide parents with a letter to request the most recent academic test scores from the teacher.

When parents visit the outpatient clinic with their children, the assessment will take place. No laboratory tests will be performed in this study, however data of the laboratory tests that were performed at timepoint of diagnosing FNAIT will be involved in this study. To gather important patient data from the pregnancy and neonatal period parents will be asked permission to obtain the medical letters from referral hospital of the child. Secondly mothers will be asked for informed consent to obtain the medical letter from the gynaecologist.

After assessment a report will be made from the observations during psychological testing.

Figure 2: Study procedures

9.4 Withdrawal of individual subjects

Subjects can leave the study at any time for any reason if they wish to do so without any consequences. The investigator can decide to withdraw a subject from the study for urgent medical reasons during the assessment.

9.4.1 Specific criteria for withdrawal

Not applicable

9.4.2 Replacement of individual subjects after withdrawal

Not applicable

9.4.3 Follow-up of subjects withdrawn from treatment

Not applicable

9.5 Premature termination of the study

In case of premature termination of the study the project leader will notify the accredited METC within 15 days, including the reasons for the premature termination.

10. SAFETY REPORTING

10.1 Temporary halt for reasons of subject safety

In accordance to section 10, subsection 4, of the WMO, the sponsor will suspend the study if there is sufficient ground that continuation of the study will jeopardise subject health or safety. The sponsor will notify the accredited METC without undue delay of a temporary halt including the reason for such an action. The study will be suspended pending a further positive decision by the accredited METC. The investigator will take care that all subjects are kept informed.

10.2 AEs, SAEs and SUSARs

10.2.1 Adverse events (AEs)

The risk on adverse events in this study negligible, therefore AEs will not be reported. If parents notify psychological burden of the assessments and notify this burden to the researchers in writing, this will be recorded and reported to the METC.

10.2.2 Serious adverse events (SAEs)

A serious adverse event is any untoward medical occurrence or effect that

- results in death;
- is life threatening (at the time of the event);
- requires hospitalisation or prolongation of existing inpatients' hospitalisation;
- results in persistent or significant disability or incapacity;
- is a congenital anomaly or birth defect; or
- any other important medical event that did not result in any of the outcomes listed above due to medical or surgical intervention but could have been based upon appropriate judgement by the investigator.

An elective hospital admission will not be considered as a serious adverse event.

The investigator will report all SAEs to the METC without undue delay after obtaining knowledge of the events.

The investigator will report the SAEs through the web portal *ToetsingOnline* to the accredited METC that approved the protocol, within 7 days of first knowledge for SAEs that result in death or are life threatening followed by a period of maximum of 8 days to complete the initial preliminary report. All other SAEs will be reported within a

period of maximum 15 days after the sponsor has first knowledge of the serious adverse events.

10.3 Follow-up of adverse events

The risk of AE in this study is negligible, therefore follow-up of AEs is not applicable. Unexpected findings or study results that might be of importance for the development or health of our subjects will be reported to the general physician.

10.4 Data Safety Monitoring Board (DSMB)

An independent Data Safety Monitoring Board (DSMB) will not be installed for this study.

11. STATISTICAL ANALYSIS

Continuous parametric data will be presented with mean \pm standard deviation (SD) or median with interquartile range (IQR) as appropriate. Categorical data will be presented as counts and percentages within each study group.

The cognitive test score of both cohorts will be compared with the Dutch average by using a linear regression model. The following potential confounders for cognitive development (IQ score) identified in earlier research will be used in the analysis;

- Sex
- Gestational age at birth
- Small for gestational age
- Neonatal morbidity
- Level of education of the parents

In second cohort; the FNAIT survivors with IVIg treatment atopic constitution and the course of infections will be assessed in a secondary analysis.

In the assessment of course of infections the following confounders will be used in the analysis by using a linear regression model;

- Day-care visit
- Smoking in a household
- Time of the year that the questionnaire was filled in

In the analysis of allergies and asthma the following confounders will be used in the analysis by using a linear regression model;

- Presence of a first degree family member with asthma eczema or allergy
- Smoking in a household

All data is analysed with IBM SPSS Statistics version 24 (IBM Software, NY, USA, 2016).

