3. OBJECTIVES

3.1 Primary objective(s)

The primary objective is to determine the cognitive test score of children diagnosed with FNAIT without and with antenatal treatment. We will assess the neurodevelopmental outcome, with IQ score as outcome measure, of two groups:

Cohort 1: To evaluate the natural history of FNAIT, we will include in this first cohort all FNAIT survivors without antenatal treatment. Our hypothesis is that the cognitive test score in this cohort will be lower compared to the general population.

Cohort 2: To evaluate the safety and benefit of IVIg treatment, the IQ score in all FNAIT survivors treated with antenatal IVIg treatment will be determined. Our hypothesis is that the cognitive test score in this cohort is similar to the general population.

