3.3 Other study parameters

We will gather the data about the following data of our cases; age and sex of the child, obstetric medical data and neonatal characteristics and morbidity of the study population. Parents will be asked to complete a questionnaire to assess the highest level of education of the parents. We use this data to describe our study population and correct for potential confounding of these factors on neurodevelopmental outcome as described in chapter 11. Study parameters are summarized in Table 1, a list of definitions can be found in Table 3.

Possible confounding factors for allergies are the family history for asthma, allergies or eczema. For evaluation of the infections it is important to assess smoking at home and day-care visit as possible confounding factors.

Table 1: Study parameters

Study parameters		
Obstetric data	Maternal characteristics	Age mother at delivery Obstetric history Medication usage during pregnancy
	Pregnancy characteristics	Gravidity/Parity Pregnancy induced hypertension Pre-eclampsia Signs of bleeding in the fetus at ultrasound
	FNAIT related therapy	IVIg treatment Intra-uterine transfusions Treatment with corticosteroids
	Labour characteristics	Mode parturition Gestational age at delivery
	Placental features	Placenta weight
Neonatal data	Birth data	Gestational age at birth Birthweight Apgar score
	Severe neonatal morbidity	Respiratory distress syndrome Perinatal asphyxia Proven early onset neonatal sepsis Retinopathy of prematurity Necrotizing enterocolitis
	Neonatal neurologic sequelae	Intracranial haemorrhage Cystic periventricular leukomalacia Ventricular dilatation Porencephalic or parenchymal cysts Convulsions Any cerebral lesions associated with adverse neurologic outcome
	Signs of bleeding	Skin manifestations Intracerebral bleeding Organ bleeding Increased bleeding tendency, reported by the caregiver
	Therapy	Platelet transfusions IVIg treatment

Table 1: Study parameters

[figure not shown]
Study parameters		
Laboratory data	HPA	HPA incompatibility HPA genotyping Anti-HPA-titre Platelet count Directly after birth Nadir Other Presence of HLA class I antibodies

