4. STUDY DESIGN

We will perform an observational cohort study. The long-term neurodevelopmental outcome of children affected by FNAIT will be evaluated. All children born between 2002 and 2017 and diagnosed with FNAIT are eligible for follow-up assessment and will be invited for an assessment at our outpatient clinic. The FNAIT survivors will be collected in two cohorts; cohort 1 will consist of FNAIT survivors without antenatal treatment, cohort 2 will consist of FNAIT survivors that were antenatally anticipated and therefore IVIg treatment to the mother was given. A summary of our study design is presented in Figure 1.

Enrollment in our study will take place via the LUMC and Stichting Sanquin Bloedvoorziening. The LUMC is national referral center for intrauterine therapy and Sanquin is national reference laboratory to diagnose FNAIT. Retrospectively FNAIT cases will be collected and asked for permission directly or via referring specialist according to the procedures described in paragraph 12.2.

After informed consent, child cognitive functioning will be assessed with a formal psychological test of cognitive functioning described in table 2, chapter 9. According to age, the parents will complete a standardized behavioral and HRQoL questionnaire. Academic performance will be assessed by collecting the most recent CITO test scores from the Dutch Pupil monitoring system developed by the National Institute for Educational Measurement [14]. Assessment of the prevalence of possible late effects of IVIg on the immune system will be assessed by questionnaires about the prevalence of allergies, asthma, eczema and course of infections by questionnaires. Parents and children, when 12 years old or older, are asked for consent to request the medical letters from the maternity or neonatology ward to obtain perinatal and neonatal data.

Figure 1: Study design

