5.4 Sample size calculation

Of note, performing sample size calculations in the context of this rare disease is difficult since literature is scarce and heterogeneous.

We performed two different sample size calculations for the two cohorts.

Cohort 1: Using the literature to date we estimated that the IQ score of FNAIT survivors without antenatal treatment is lower, that is 92 versus average (100) in the normal population. To show a difference in IQ score between FNAIT survivors without IVIg treatment compared to a fixed average of 100, we performed a sample size calculation for a one-sample t-test. We calculated that a minimum group size of 39 was needed to show a mean difference of 7 IQ points with a power of 0.8 and a significance of 0.05. We assume a standard deviation (SD) of 15 for the IQ score.

Cohort 2: In the FNAIT survivors with antenatal treatment we expect no difference in IQ score between cases and the national average. To show that there is no difference IQ score in anticipated IVIg treatment compared to the Dutch average we perform a non-inferiority calculation by a one-sample t-test. In this case we need a sample size of 39 children with a non-inferiority margin of 7 IQ points, with a power of 0.8 and a significance level of 0.025. We assume a standard deviation (SD) of 15 for the IQ score.

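### Section 11 does not carry over the one-sample tests, alpha levels and cohort 2 margin of section 5.4, and its five-covariate regression cannot give the adjusted comparison the protocol promises.

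*Combined protocol and SAP*

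**What the plan says.** **Sizing (section 5.4).** For cohort 1 (no antenatal treatment), IQ is "compared to a fixed average of 100, we performed a sample size calculation for a one-sample t-test", with a 7-point difference, power 0.8, significance 0.05 and SD 15. For cohort 2 (antenatal IVIg), IQ is "compared to the Dutch average we perform a non-inferiority calculation by a one-sample t-test", using "a non-inferiority margin of 7 IQ points, with a power of 0.8 and a significance level of 0.025" and the same SD. Each calculation gives 39 children.

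**Hypothesis (section 3.1).** For cohort 2: "Our hypothesis is that the cognitive test score in this cohort is similar to the general population".

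**Analysis (section 11).** One method serves both cohorts: "The cognitive test score of both cohorts will be compared with the Dutch average by using a linear regression model". Then: "The following potential confounders for cognitive development (IQ score) identified in earlier research will be used in the analysis". The five are sex, gestational age at birth, small for gestational age, neonatal morbidity and parental education. For this comparison the section gives no t-test, margin, alpha, sidedness, confidence-interval rule, named coefficient, or coding or centring of covariates.

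**Adjustment (section 3.3).** Baseline data will be used to "correct for potential confounding of these factors on neurodevelopmental outcome as described in chapter 11".

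**Who is studied (section 4).** "The FNAIT survivors will be collected in two cohorts; cohort 1 will consist of FNAIT survivors without antenatal treatment"; cohort 2 is the IVIg-treated group. No reference or control children are described anywhere.

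**The concern.** A regression fitted to one cohort has no comparison-group coefficient. It can be set against a population average only through its intercept or through a prediction at chosen covariate values. Section 11 specifies neither, and the choice decides what is estimated and how precisely. The sample size of 39 and its power belong to the tests in section 5.4, not to an unnamed regression parameter.

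The stake is greatest in cohort 2, where section 3.1 ties the IQ comparison to the safety and benefit of IVIg. The 7-point limit that would decide the question stands in the sample size section, and the analysis section does not refer to it. Two analysts could follow section 11 faithfully and reach different conclusions, and the choice could be made after the data are seen.

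**Working it through.** **Inputs from section 5.4:** n = 39, SD 15, difference or margin 7, alpha 0.05 (cohort 1) and 0.025 (cohort 2). **From section 11:** five covariates. Counting each as one term gives six parameters and 39 − 6 = 33 residual degrees of freedom. **Not in the documents, so assumed:** the share of IQ variance explained by the covariates (R², 0% to 30%) and the covariate distributions used in step 4.

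**1. The plan's own figure.** Exact one-sample t power from the noncentral t, noncentrality (7/15)·√n:
- n = 38 gives 0.7999 and n = 39 gives 0.811, for two-sided 0.05 and for one-sided 0.025. Both stated sample sizes reproduce.
- One-sided 0.05 would need only 30, so the cohort 1 figure implies a two-sided test.
- The planned 95% half-width is 2.0244 × 15/√39 = 2.0244 × 2.402 = 4.86 points.

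**2. Covariates centred at the cohort's own means: estimate and power.** Least squares then makes the intercept equal to the raw cohort mean, so nothing has been adjusted. With residual SD 15 and 33 degrees of freedom, power at 7 points is 0.807, against 0.811.

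**3. The same model: error rate.** If the 39 children are a sample of FNAIT survivors, as the t-test takes them to be, the mean has variance 15²/39. The regression standard error uses only the residual part, 15²(1 − R²)/39. At a true mean exactly on the margin,

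one-sided error = P(t₃₃ > 2.0345·√(1 − R²)).

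| Assumed R² | Cut-off | One-sided error |
|---|---|---|
| 0% | 2.035 | 2.5% |
| 10% | 1.930 | 3.1% |
| 20% | 1.820 | 3.9% |
| 30% | 1.702 | 4.9% |

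Simulation with 300,000 draws per row gave 2.54%, 3.11%, 3.91% and 4.95%. The one-sample t-test on the same data stayed between 2.50% and 2.55%.

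**4. Any other covariate profile.** The estimate is now the predicted IQ at that profile, not the cohort mean. Its standard error is 15·√(1/39 + d′(Z′Z)⁻¹d), where Z holds the centred covariates and d is the profile's distance from the cohort means. Half-width = 2.0345 × SE.

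The documents give no covariate distribution, so this is direction only. Assumed cohort: sexes equal; gestational age mean 37.5 weeks, SD 2; small for gestational age 15%; neonatal morbidity 15%; three equally likely education levels as one linear term; residual SD 15. Every profile except the last takes middle education. Median SE over simulated cohorts:

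| Profile | SE | Half-width |
|---|---|---|
| Cohort gestational age, sexes averaged, not small, no morbidity | 2.92 | 5.9 |
| Same, one sex | 3.85 | 7.8 |
| Population-like: 39.5 weeks, 10% small, 3% morbidity, sexes averaged | 3.72 | 7.6 |
| 40 weeks, not small, no morbidity, sexes averaged | 4.35 | 8.8 |
| All covariates at zero (uncentred) | about 49 | about 100 |

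If the profile's true IQ equals the norm, power to clear the 7-point margin is about 45% in the third row, 35% in the fourth and 3% in the last. The last row is the prediction for a birth at 0 weeks and has no meaning.

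**The case against.** Several points on the other side have force.

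- **The margin is still pre-specified.** A reader might infer that section 11 replaces or revokes it. The documents do not support that: section 11 is silent, and section 5.4 of the same document fixes the margin and its alpha. The gap is that no analysis rule uses them.
- **Regression is not incompatible with section 5.4.** An intercept-only regression of IQ minus 100 is the one-sample t-test. The confounders come in a separate sentence, so an unadjusted comparison followed by an adjusted one is a possible reading. It is not stated, and the adjusted step would still need population values that the protocol does not give. A reader might also infer a general loss of power, but step 2 shows almost none with mean centring.
- **The inflated error depends on viewpoint and on an assumed R².** If inference is conditional on these children's covariates, the smaller standard error is legitimate and appears as a power gain (84.6% to 92.2% at R² of 10% to 30%). That is not the inference the t-test in section 5.4 makes.
- **Nothing says that similarity will be read from a non-significant difference.** A reader might infer it from the missing margin, but no section states such a rule, and this point does not rest on it.
- **The study is observational, and the mean and SD are to be reported as appropriate,** so a reader could do the section 5.4 check by hand. True, but that does not make it the planned primary analysis.

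**Conclusion.** The point holds as under-specification of the primary analysis in both cohorts, most serious for the cohort 2 conclusion. The sample sizes are arithmetically correct. What is missing is the link from them to the analysis, together with any stated parameter for the regression to test.

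As written, the five-covariate model yields one of two things. The first is the unadjusted mean, with power nearly intact but one-sided error of 3.1% to 4.9% instead of 2.5%, assuming R² of 10% to 30% and sampled children. The second is the IQ of one covariate profile, to which n = 39 and its power do not apply; the half-width is about 6 to 8 points at plausible profiles, against 4.86. Neither delivers both the powered test and the correction promised in section 3.3. The profile figures rest wholly on assumed covariate distributions; the other conclusions about what is estimated do not.

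**What to change.** In section 11, state the primary analysis for each cohort as mean IQ minus the norm mean, with a two-sided 95% confidence interval from a one-sample t-test (or, equivalently, an intercept-only regression):

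- **Cohort 1:** a deficit is shown if the upper limit is below 0.
- **Cohort 2:** non-inferiority is shown if the lower limit is above −7 (one-sided 0.025, as in section 5.4).

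State the norm mean. Section 5.4 gives 100 for cohort 1 but only the Dutch average, without a value, for cohort 2. Three instruments are used, and the reference list marks only the WPPSI-III as a Dutch edition. The sponsor should confirm that 100 is the Dutch norm mean for all three instruments and for cohort 2.

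Keep the five-covariate regression as supportive. Name its tested parameter and the value at which each covariate is centred. Call it adjusted to the Dutch population only if population covariate values are stated.

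**Cost:** wording only, with no extra children. The downside is that the primary estimate is then openly unadjusted. If the sponsor wants an adjusted primary comparison, population values for the five covariates must be obtained and the sample size reconsidered for that parameter.

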9.1.2 Secondary study parameters/endpoints

NDI is a composite outcome of:

- Cerebral palsy \geq grade II according to Gross Motor Classification System (GMFCS) [19]
- Impaired cognitive, language and/or motor development (test scores <70)
- Bilateral blindness and/or bilateral deafness
- Bilateral deafness requiring amplification

The Health Related Quality of life will be assessed with PedsQL and behavioral problem score will be assessed using the Child Behavior Checklist [20, 21].

Academic performance will be evaluated by obtaining test scores from the Dutch Pupil monitoring system. [14] The latest test scores from primary school will be requested. If children are in high school grades from grade 6 in primary school will be used in our evaluation to obtain uniform test scores. Three academic domains will be assessed; arithmetic and spelling performance and measurements on reading comprehension. Of these three domains the following scores will be obtained from the monitoring system; the raw test scores, standardized test scores and the level of the child.

To assess long-term effects of maternal IVIg treatment on the immune system of the child we will assess two outcome parameters:

- The prevalence of allergies, asthma and eczema will be evaluated by a questionnaire composed in collaboration with an allergist. The severity and control of the allergic rhinitis will be assessed by the CARATkids questionnaire [22].

- The prevalence of children with an abnormal incidence or frequency of infections will be assessed by a questionnaire based on the guideline; 'Richtlijn diagnostiek naar onderliggende aandoeningen bij kinderen met recidiverende luchtweginfecties' [23] and the 10 warning signs of PI of the Jeffrey Model Foundation. [24]

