9.1.3 Other study parameters

An inventory will be made of the following confounders gender, obstetrical and neonatological complications and education level of the parents according to the International Classification of Education. [25] We will assess the family history of allergies asthma and eczema to obtain information about possible confounding factors in our study groups. Also smoking and day-care visit will be questioned.

Table 2: Overview assessments

Study assessments			
Age group	Name assessment tool	Abbreviation	Outcome
Cognitive development			
2-3 years	Bayley scales of infant and toddler development third edition.	Bayley III	IQ score
4-6 years	Wechsler Preschool and Primary Scale of Intelligence third edition.	WPPSI III	IQ score
7-16 years	Wechsler Intelligence Scale for Children fifth edition	WISC V	IQ score
Motor development			
2-3 years	Bayley scales of infant and toddler development third edition	Bayley III	Motor test score
2-18 years	Neurologic Examination According to Touwen.	Touwen	Gross Motor Function Classification System
Quality of life			
5-7 years	Pediatric Quality of Life Inventory	PedsQoL	Health related quality of life score
8-12 years	Pediatric Quality of Life Inventory	PedsQoL	Health related quality of life score
Behaviour			
1.5-5 years	Child Behavior Checklist	CBCL	Behaviour test score
6-18 years	Child Behavior Checklist	CBCL	Behaviour test score
Course of infections			
2-18 years	Questionnaire based on 'Richtlijn diagnostiek naar onderliggende aandoeningen bij kinderen met recidiverende luchtweginfecties'		Indication for diagnostic evaluation by immunologist; Yes/No.

Table 2: Overview assessments

Study assessments			
Age group	Name assessment tool	Abbreviation	Outcome
Atopic constitution			
2-18 years	Questionnaire composed in collaboration with allergist ([name]).	(Parent reported)	Allergy
Severity of asthma and hay fever			
6-18 years	Control of allergic rhinitis and asthma test.	CARATkids	CARATkids score

Table 3: Definitions of outcome

Definitions of outcome		(1/3)
Outcome parameter	Definition	
Obstetric medical data		
Pregnancy induced hypertension	De novo hypertension (blood pressure above 140/90 mmHg) after gestational week 20.[26]	

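### Section 11 names no comparator for infections and atopy: covariate-only regressions in an all-IVIg cohort cannot estimate the IVIg effect that the protocol sets out to assess

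*Combined protocol and SAP*

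**What the plan says.** **Aim.** Section 9.1.2 introduces these outcomes with "To assess long-term effects of maternal IVIg treatment on the immune system of the child we will assess two outcome parameters". The items beneath it are worded as prevalences. The first is "The prevalence of allergies, asthma and eczema will be evaluated by a questionnaire composed in collaboration with an allergist"; the second is the proportion of children with an abnormal infection history. Section 3.2 likewise joins a focus on IVIg side effects to finding out how common these conditions are.

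**Population.** Section 11 states: "In second cohort; the FNAIT survivors with IVIg treatment atopic constitution and the course of infections will be assessed in a secondary analysis". Section 1 defines cohort 2 as children with anticipated disease whose mothers were given IVIg.

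**Models.** For infections, Section 11 says "In the assessment of course of infections the following confounders will be used in the analysis by using a linear regression model" and lists day-care, household smoking and time of year. For atopy it says "In the analysis of allergies and asthma the following confounders will be used in the analysis by using a linear regression model" and lists first-degree family history and household smoking. Eczema is not named in either sentence, although atopic constitution may be meant to cover it.

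**Reference values and description.** The only reference in Section 11 belongs to IQ: "The cognitive test score of both cohorts will be compared with the Dutch average by using a linear regression model". For description, "Categorical data will be presented as counts and percentages within each study group".

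**Outcome types.** Table 2 records the infection outcome as yes or no. Table 3 defines allergy and eczema by parent report, and poor control of rhinitis or asthma by a cut-off. The CARATkids score is numeric and is collected from age 6.

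**The concern.** An effect needs something to be compared with. In a cohort where every child was exposed, a prevalence cannot by itself be attributed to the exposure, and regressing the outcome on day-care or smoking does not change that.

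The consequence is practical. Section 1 says the long-term safety of IVIg in this disease has not been evaluated, and Section 3.2 makes its side effects a focus. With no comparator written down, the choice between cohort 1, the general population and no comparison at all could be made after the results are known. A cohort 2 percentage could also be presented as reassurance, or as a signal, without an analysis that supports either.

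A smaller matter goes with it. Linear regression is named for outcomes that are mostly yes/no, and the plan mentions neither a binary-outcome model nor robust standard errors.

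**Working it through.** **1. The plan's own figure.** The only sample size is for IQ (Section 5.4): 39 per cohort, with a difference or margin of 7, SD 15 and power 0.8. Normal approximation: (15 × (1.960 + 0.842) / 7)² = 36.0, rounded up to 37. The exact one-sample t calculation gives 39 for cohort 1 (two-sided 0.05) and 39 for cohort 2 (one-sided 0.025), with 81.1% power at 39. The figure reproduces and is not in dispute. No size, rate or reference prevalence is given for infections or atopy.

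**2. Can the written model return an IVIg effect?** The infection model has four columns: intercept, day-care, smoking and season (taken as one term). In cohort 2 an IVIg indicator equals 1 for every child, so it duplicates the intercept. Adding it gives five columns of rank 4, and its coefficient is not estimable. With both cohorts the same five columns have rank 5, and it is. The atopy model fails in cohort 2 for the same reason.

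**3. Does another section supply the contrast?**
- Section 3.1 states its hypotheses against the general population, for the cognitive score only.
- Section 5.1 plans to describe IVIg dosage, not to model it.
- Section 9.1.3 says "We will assess the family history of allergies asthma and eczema to obtain information about possible confounding factors in our study groups". This hints at a comparison between cohorts but does not specify one.
- The infection guideline in Tables 2 and 3 classifies each child; it is not a reference prevalence.

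None of these supplies the contrast.

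**4. Scale.** Assumptions: 39 children per cohort, and prevalences of 5%, 10% and 20%.
- Exact interval for k of n: lower limit Beta(0.025; k, n−k+1), upper limit Beta(0.975; k+1, n−k).
- Half-width of a between-cohort risk difference (Wald): 1.96 × √(2p(1−p)/39). At 10% this is 1.96 × √(0.18/39) = 0.133.
- Power for a doubling between cohorts: pooled z-test, two-sided 0.05.
- Power for a doubling against a fixed reference: exact binomial in cohort 2, upper tail at most 0.025, rejecting at 6, 9 or 14 events or more. The reference is treated as known without error.

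| Assumed prevalence | Expected events (39p) | Exact 95% CI, cohort 2 | Half-width, cohort difference | Power, cohort 2 v 1 | Power, cohort 2 v fixed reference |
|---|---|---|---|---|---|
| 5% | 1.95 | 2/39: 0.6% to 17.3% | 9.7 points | 13% | 19% |
| 10% | 3.9 | 4/39: 2.9% to 24.2% | 13.3 points | 23% | 38% |
| 20% | 7.8 | 8/39: 9.3% to 36.5% | 17.8 points | 49% | 75% |

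The Newcombe score method, which is safer with few events, gives half-widths of 12.3, 14.7 and 17.9 points for 2, 4 and 8 events per cohort.

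**5. Load on the written infection model.** Three covariate coefficients share 1.95, 3.9 or 7.8 expected events: 0.65, 1.3 or 2.6 events each. None of the three is IVIg.

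**The case against.** The best defence is that the objective is largely descriptive. Sections 3.2, 4 and 9.1.2 all use the language of prevalence, and Section 11 delivers percentages. This stands in part: the prevalence element is met. But the lead-in in Section 9.1.2 promises an assessment of effects, and covariate-adjusted regressions serve no purpose in a purely descriptive plan.

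A second defence is that a comparison of the cohorts was meant. The regression sentences do not repeat the restriction to cohort 2, they call the covariates confounders, and Sections 4 and 9.3 do not limit the questionnaires to one cohort. That may be so, and a reader should not infer that the plan rules a comparison out. A crude difference could be read from the per-group percentages. What is missing is a named contrast, an effect measure and an adjustment.

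Two stronger readings are tempting and do not hold.
- A reader might infer that cohort 1 is the comparator the plan needs. Every comparison actually written is with the population, and the two one-sample calculations in Section 5.4 follow the same logic. The cohort contrast also cannot be separated from index versus anticipated disease, and Tables 1 and 3 record IVIg given after birth, so cohort 1 children may not all be free of IVIg.
- A reader might infer that linear regression is invalid here. Least squares on a yes/no outcome can give a valid risk difference if the standard errors are robust, and it suits the CARATkids score. The gap is that Section 11 does not say which is intended.

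**Conclusion.** The concern holds in a limited form. As written, the infection and atopy models cannot estimate an IVIg effect, and no other section names a comparator. This follows from the structure of the plan and rests on no assumed rate. The descriptive part of the objective is met.

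The figures on precision do rest on assumptions: 39 is a minimum set for IQ, all eligible children are to be invited, and the documents give no prevalences. Under those assumptions any contrast is imprecise and can only be exploratory. A reader might take the gap as undermining the study's safety conclusions in general. The documents do not support that: Section 3.1 evaluates the safety and benefit of IVIg through IQ, these are secondary outcomes, and the IQ analyses do not depend on them. The point should be fixed before the data are analysed, but it does not threaten the primary analysis.

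**What to change.** In Section 11, name the comparator before the data are analysed. Either of the following closes the gap, and both may be reported:

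- **(a) Cohort 2 versus cohort 1.** Analyse infections, allergy, asthma and eczema in both cohorts with a cohort term. Report the risk difference with a 95% CI, adjusted for the listed covariates only as far as the number of events allows. State that the contrast cannot be separated from index versus anticipated status.
- **(b) Cohort 2 versus a named Dutch reference prevalence**, in line with the IQ analysis. State whether the reference was measured in a comparable way.

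For the yes/no outcomes, specify a binary-outcome model or a linear model with robust standard errors. Keep linear regression for the CARATkids score and note that it covers only children aged 6 and over. Label the result exploratory.

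If only description is intended, delete the two regressions and the wording about effects in Section 9.1.2, and report prevalences with exact CIs.

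The cost is wording in Section 11 and analysis of questionnaires already planned. It should be checked whether SPSS 24 offers the chosen model, and other software named if it does not. The drawback is low precision under either option. In addition, (a) carries the confounding described above, and (b) depends on comparability, which is uncertain because the allergy questionnaire was put together with an allergist rather than taken from a reference survey named in the plan.
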